### 8.2.2 Pharmacology

Mode of Action:

Absorbed systemically; binds to nicotine receptors thereby reducing withdrawal symptoms (including nicotine craving) associated with smoking cessation. Nicotine lozenges deliver nicotine at a lower and steadier rate compared to smoking cigarettes through the oral mucosa as opposed to the skin or gastrointestinal tract.

Excretion: Urine

### 8.2.3 Storage and Stability

Store at 20-25°C (68-77°F).

Keep lid tightly closed and protect from light

### 8.2.4 Administration

See package insert for complete details for specific product used.

Dosing is determined by the time to patients' first cigarette after waking up.

Smokers who smoke first cigarette within 30 minutes of waking up:

- Use one 4-mg lozenge every 1 to 2 hours for weeks 1 to 6, followed by one 4-mg lozenge every 2 to 4 hours for weeks 7 to 9, then one 4-mg lozenge every 4 to 8 hours for weeks 10 to 12.

Smokers who smoke their first cigarette > 30 minutes after waking up:

- Use one 2-mg lozenge every 1 to 2 hours for weeks 1 to 6, followed by one 2-mg lozenge every 2 to 4 hours for weeks 7 to 9, then one 2-mg lozenge every 4 to 8 hours for weeks 10 to 12.

Patient is advised to pick "quit day" and begin using nicotine polacrilex lozenge on that day and simultaneously stop smoking. They may continue to smoke if not immediately able to/willing to stop smoking, however every effort should be made to decrease the amount smoked while on replacement therapy, as continued smoking can increase adverse effects. It is important for patients to complete the full program, but some may need to use NRT for longer periods to keep from smoking.

Place the lozenge in your mouth and allow the lozenge to slowly dissolve (20 - 30 minutes). Avoid chewing or swallowing the lozenge. Patients should also avoid eating or drinking 15 minutes before using or while the lozenge is in your mouth.

Patients may experience a tingling sensation in their mouth when using the lozenge. While using the lozenge occasionally move the lozenge from one side of your mouth to the other until completely dissolved.

To improve your chances of quitting, use at least 9 lozenges per day for the first 6 weeks

Avoid using more than one lozenge at a time or continuously use one lozenge after another since this may cause hiccups, heartburn, nausea or other side effects. Do not use more than 5 lozenges in 6 hours or 20 lozenges per day.

#### 8.2.5 Availability/How Supplied

Nicotine polacrilex lozenges are FDA approved for smoking cessation aid and are commercially available.

Product is supplied as a 2 mg or 4 mg oral lozenge or troche.

#### 8.2.6 Side Effects

There are no significant safety concerns associated with using more than 1 over-the-counter (OTC) nicotine replacement therapy (NRT) simultaneously or at same time as another nicotine-containing product (including cigarettes), however the potential for nicotine overdose is increased if patient continues to smoke. Every effort should be made to decrease the number of cigarettes smoked to zero while using replacement therapy.

Below are the most commonly reported adverse events related to nicotine lozenge. Please refer to the package insert/investigator's brochure for the comprehensive list of adverse events.

Gastrointestinal symptoms (nausea, vomiting, abdominal pain, diarrhea, unpleasant taste), arthralgia, jaw pain, myalgia, dizziness, lightheadedness, headache, insomnia, hiccups

Contact your doctor if you experience these side effects and they are severe or bothersome.

The incidence of developing dependence on nicotine replacement is considered to be very low. Smokers may worry that they will become dependent on nicotine replacement, but nicotine dependence rarely occurs. Nicotine replacement therapy has not been shown to increase or cause development of cancer.

Use of nicotine polacrilex lozenges may not be appropriate in the following populations and should be carefully monitored by a physician:

- non-smokers, occasional smokers, and children under 18 years of age (see Warnings),
- known hypersensitivity of the skin, allergy to nicotine or any patch components,
- generalized skin disorders,
- recovery phase of acute myocardial infarction, unstable or worsening angina pectoris, severe cardiac arrhythmias, and recent cerebrovascular accident.

Pregnancy and Breastfeeding:

Nicotine Polacrilex is considered US FDA Category C. The adverse effects on fetal and maternal health caused by cigarette smoking are clearly established. Nicotine freely passes into the placenta and is found in both amniotic fluid and umbilical cord blood (Luck & Nau, 1984; Hibberd et al, 1978). Nicotine is readily transferred to the fetus throughout pregnancy; the fetus is actually exposed to higher nicotine concentrations than the mother (Luck et al, 1985). Nicotine use during the third trimester of pregnancy has been associated with diminished fetal breathing movements possibly due to decreased placental perfusion.

If you are pregnant or breast-feeding, only use this medicine on the advice of your health care provider. Smoking can seriously harm your child. Try to stop smoking without using any nicotine replacement medicine. This medicine is believed to be safer than smoking. However, the risks to your child from this medicine are not fully known.

#### 8.2.7

#### Potential Interactions

There is increased risk of nicotine overdose in patients who continue smoking while using a nicotine replacement therapy, or those utilizing more than one form of nicotine replacement therapy. Caution should be used to prevent overdose, and smoking should be completely discontinued while using therapy.

Signs and symptoms of nicotine overdose may include: abdominal or stomach pain, vomiting, cold sweat, confusion, headache, convulsions (seizures), disturbed hearing and vision, drooling, extreme exhaustion, pale skin, rapid heartbeat, and tremors. Contact your doctor if you experience any of these symptoms.

## 9. Statistical Considerations

### 9.1 Estimated Effect Size

Based on our current trial preliminary findings (Preliminary Studies) and previous trial with low SES smokers, we conservatively estimate 7-day point-prevalence tobacco abstinence at 6-month follow-up will be 15% for the standard care group and 32% for the intervention group. This estimate is based on our current trial, which has a higher intensity control group.

### 9.2 Power calculation:

#### 9.2.1 Aim 1. Primary effectiveness outcome.

The study will have 80% power to detect a 17% difference in 7-day point-prevalence tobacco abstinence with a two-sided significance level of 0.01 with 280 participants.

#### **Numeric Results for Testing Two Proportions using the Z-Test with Unpooled Variance**

H0:  $P1 - P2 = 0$ . H1:  $P1 - P2 = D1 \neq 0$ .

Target	Actual	Diff						
		Power	Power* N1	N2	N	P1	P2	D1
0.80	0.80400	117	117	234	0.2700	0.1000	0.1700	0.0100
0.90	0.90042	148	148	296	0.2700	0.1000	0.1700	0.0100
0.80	0.80014	78	78	156	0.2700	0.1000	0.1700	0.0500
0.90	0.90167	105	105	210	0.2700	0.1000	0.1700	0.0500
0.80	0.80045	126	126	252	0.2900	0.1200	0.1700	0.0100
0.90	0.90130	161	161	322	0.2900	0.1200	0.1700	0.0100
0.80	0.80185	85	85	170	0.2900	0.1200	0.1700	0.0500
0.90	0.90186	114	114	228	0.2900	0.1200	0.1700	0.0500
0.80	0.80184	140	140	280	0.3200	0.1500	0.1700	0.0100
0.90	0.90061	178	178	356	0.3200	0.1500	0.1700	0.0100
0.80	0.80115	94	94	188	0.3200	0.1500	0.1700	0.0500
0.90	0.90119	126	126	252	0.3200	0.1500	0.1700	0.0500
0.80	0.80095	148	148	296	0.3400	0.1700	0.1700	0.0100
0.90	0.90146	189	189	378	0.3400	0.1700	0.1700	0.0100
0.80	0.80289	100	100	200	0.3400	0.1700	0.1700	0.0500
0.90	0.90024	133	133	266	0.3400	0.1700	0.1700	0.0500
0.80	0.80043	159	159	318	0.3700	0.2000	0.1700	0.0100
0.90	0.90101	203	203	406	0.3700	0.2000	0.1700	0.0100
0.80	0.80088	107	107	214	0.3700	0.2000	0.1700	0.0500
0.90	0.90015	143	143	286	0.3700	0.2000	0.1700	0.0500

\* Power was computed using the normal approximation method.

- 9.2.2 Aim 1. Secondary effectiveness outcome 1.  
For biochemically-confirmed 7-day point prevalence abstinence at 3-months, with a sample size of 140 in each arm then smallest detectable difference will be 18% with 80% power and a Bonferroni corrected alpha of 0.002 using and an estimated control rate of 20%.
- 9.2.3 Aim 1. Secondary effectiveness outcome 2.  
For self-reported 7-day point prevalence abstinence at 6-months, with a sample size of 140 in each arm then smallest detectable difference will be 22% with 80% power and a Bonferroni corrected alpha of 0.002 using and an estimated control rate of 31%.
- 9.2.4 Aim 1. Secondary effectiveness outcome 3.  
For self-reported 7-day point prevalence abstinence at 3-months, with a sample size of 140 in each arm then smallest detectable difference will be 22% with 80% power and a Bonferroni corrected alpha of 0.002 using and an estimated control rate of 28%.
- 9.2.5 Aim 1. Secondary effectiveness outcome 4.  
For continuous abstinence, with a sample size of 140 in each arm then smallest detectable difference will be 21% with 80% power and a Bonferroni corrected alpha of 0.002 using and an estimated control rate of 20%.
- 9.2.6 Aim 1. Secondary effectiveness outcome 5.  
For sustained abstinence, with a sample size of 140 in each arm then smallest detectable difference will be 19% with 80% power and a Bonferroni corrected alpha of 0.002 using and an estimated control rate of 13%.
- 9.3 Estimate of drop-outs/loss to follow-up:  
We estimate that 10% of participants will die within 6-months of enrollment, so an additional 10% (n=28) will be recruited.
- 9.4 Total Sample size:  
308 patient participants.
- 9.5 Plans for handling missing data:  
At the outset, we will examine the frequency distributions of all variables. Data from all sites will be pooled for analysis, after confirming there is no significant heterogeneity among sites or adjusting as needed. We will compare the baseline characteristics to assess whether randomization distributed covariates evenly. Outcome analyses will be intent-to-treat; we will classify participants who are lost to follow-up and those who do not provide a saliva or an expired air sample as current smokers. We will determine whether there is differential dropout in the groups and consider developing probability-of-completion weights to obtain unbiased estimates of treatment effect. We will assess whether data are missing at random. We will perform sensitivity analysis using: 1) a complete case analysis and 2) multiple imputation for missing data.

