9.7 Plans for analyzing the secondary objectives: secondary treatment effectiveness (Aim 1)

The 5 secondary objectives (defined in Section 2.3) include various ways of measuring abstinence at different times of assessment. In order to adjust for multiple comparisons, differences will be considered significant at  $0.01/N=0.01/5=0.002$  level.

Similar to the primary objective is to compare the proportions of participants in the study arms with 7-day point-prevalence abstinence from cigarettes at 3-months post enrollment. We will define 7-day point-prevalence by saliva cotinine (< 15 ng/ml) or expired air CO (< 10 ppm). All participants who report being quit and no NRT or e-cigarette use will be requested to provide saliva samples, expired air CO will be measured in participants who report being quit and report concurrent NRT or e-cigarette use. If a participant is lost to follow-up or does not provide a saliva or CO sample, they will be considered a current smoker. Chi-square tests will be used to compare the outcomes between treatment groups.

Another secondary objective is to compare the proportions of participants in the study arms that self-report cigarette abstinence at 3-months. The participant will be asked, "In the past 7 days, have you smoked a cigarette, even a puff." With the answer recorded as "Yes" or "No". If the self-report response is unavailable, the participant will be considered a current smoker. Chi-square tests will be used to compare the outcomes between treatment groups. The process will be repeated using self-reported cigarette abstinence at 6-months.

Another secondary objective is to compare the proportions of participants in the study arms that report a continuous abstinence at 6 months. The participants will be asked, "How long has it been since you last smoked a cigarette (even one or two puffs)?" at 6 months. If the response is more than or equal to 3 months (e.g. time since previous survey), the participant will be considered having a continuous abstinence at 6 months. If the self-report response is unavailable, the participant will be considered not having a continuous abstinence at 6 months. Chi-square tests will be used to compare the outcomes between treatment groups.

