Another secondary objective is to compare the proportions of participants with sustained abstinence at 6 months. To qualify as a sustained abstinence at 6 months, the participant must qualify as biochemically-verified 7-day point prevalence cigarette abstinence at 3 and 6 months, using the definition above. If either measure is not available the participant will not be considered sustained abstinence at 6 months. Chi-square tests will be used to compare the outcomes between treatment groups.

Generalized Estimating Equations (GEE) approach will be used to study the treatment effect over time, incorporating 3 & 6 month follow-up data. This will take into account the repeated measures structure of observations within the same individuals over time and allow for analysis of incomplete data across time.

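### Section 9.2.2 states an 18-point detectable difference where the plan's own formula gives 21 points, as Section 9.2.5 states from the same inputs; power for 18 points is about 60%, not 80%

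*Combined protocol and SAP*

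**What the plan says.** Section 9.2.2 covers the first secondary outcome: "For biochemically-confirmed 7-day point prevalence abstinence at 3-months, with a sample size of 140 in each arm", the "smallest detectable difference will be 18% with 80% power and a Bonferroni corrected alpha of 0.002 using and an estimated control rate of 20" per cent.

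Section 9.2.5 covers the fourth: "For continuous abstinence, with a sample size of 140 in each arm", the "smallest detectable difference will be 21% with 80% power and a Bonferroni corrected alpha of 0.002 using and an estimated control rate of 20" per cent.

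Section 9.2.6, for sustained abstinence, also at 140 per arm, states that the "smallest detectable difference will be 19% with 80% power and a Bonferroni corrected alpha of 0.002 using and an estimated control rate of 13" per cent.

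Section 9.7 sets one threshold for all five secondary outcomes: "differences will be considered significant at $0.01/N=0.01/5=0.002$ level". It compares the arms with chi-square tests. It also defines sustained abstinence so that "the participant must qualify as biochemically-verified 7-day point prevalence cigarette abstinence at 3 and 6 months".

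The table in Section 9.2 is headed as an unpooled-variance Z-test for two proportions, with a footnote that power was computed by the normal approximation. Section 9.2.1 makes the primary test two-sided at 0.01. Sidedness is not restated for the secondary outcomes.

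**The concern.** For a two-proportion comparison, the number per arm, the power, the alpha with its sidedness and the control rate together fix the smallest detectable difference. Sections 9.2.2 and 9.2.5 print the same values for all of these and arrive at 18 and 21 points. No further input in the documents separates them.

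Section 9.2.2 is the plan's only power statement for verified abstinence at 3 months taken alone. If 18 is the wrong figure, the plan claims 80% power for a difference that it would miss much more often than one time in five. A reader of a non-significant 3-month result would then think the trial more sensitive than it was.

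**Working it through.** **Inputs.** 140 per arm, 80% power, alpha 0.002 and control rate 20% (9.2.2 and 9.2.5). Alpha = 0.01/5 = 0.002 (9.7). Two-sided testing is carried over from 9.2.1 as an assumption. Method: unpooled Z, normal approximation (table in 9.2).

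**Formula.** With difference d = p1 − p2 and n per arm,

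power = Φ( d / √[(p1(1−p1) + p2(1−p2))/n] − z(1−α/2) ).

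**Step 1: reproduce the plan's own figures.**

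- Primary row, 32% v 15%, n = 140, alpha 0.01: standard error √[(0.2176 + 0.1275)/140] = 0.04965; 0.17/0.04965 = 3.424; 3.424 − 2.576 = 0.848; power 0.80184, as printed.
- 37% v 20%, n = 159, alpha 0.01: power 0.80043, as printed.

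**Step 2: solve for the detectable difference at alpha 0.002 (z = 3.090), n = 140, 80% power.**

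| Section | Control rate | Formula (points) | Stated |
|---|---|---|---|
| 9.2.2 | 20% | 21.07 | 18 |
| 9.2.3 | 31% | 22.60 | 22 |
| 9.2.4 | 28% | 22.33 | 22 |
| 9.2.5 | 20% | 21.07 | 21 |
| 9.2.6 | 13% | 19.12 | 19 |

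Four of the five figures agree once decimals are dropped. Section 9.2.2 is 3 points out.

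**Step 3: power for the stated 18 points (38% v 20%) at n = 140.** Standard error √[(0.2356 + 0.1600)/140] = 0.05316; 0.18/0.05316 = 3.386; 3.386 − 3.090 = 0.296; power 61.6%. Exact enumeration of the chi-square test that 9.7 plans gives 59.6%. By the plan's formula, 80% power for 18 points needs 189 per arm. For 21 points at n = 140, power is 79.7%, so 9.2.5 holds.

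**Step 4: look for a reading that rescues 18.**

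- *More patients analysed.* Sections 9.3 and 9.4 recruit 308, or 154 per arm. Assuming 147 per arm (halfway between 140 and 154), power for 18 points is 64.8% (exact 63.0%). Assuming all 154, it is 67.8% (exact 66.1%), and the detectable difference is 20.0 points.
- *One-sided 0.002.* 19.9 points.
- *Other approximations, two-sided 0.002.* Pooled variance 21.6, arcsine 21.4, continuity-corrected 22.3 points. All lie further from 18.
- *Uncorrected alpha 0.01.* 18.2 points, with 79.1% power for 18 points. This fits, but 9.2.2 itself says that 0.002 was used.
- *A lower control rate at alpha 0.002.* A rate of 10.1% gives 18.0 points. If decimals are dropped, as in the other four statements, rates from 10.1% to just under 12.7% would all print as 18.

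**The case against.** Four points can be made on the other side.

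First, the consequence is small. The total of 280, or 308 with the allowance for deaths, rests on the primary row, which reproduces exactly. No decision rule or analysis uses the 18%. That stands and limits the weight of the point. It does not remove a direct contradiction between two statements in the same section.

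Second, calling the other four figures correct relies on dropping decimals, a convention the plan does not state. By ordinary rounding, 9.2.3 (22.60) would read 23, and power for its stated 22 points is 76.9%. That is fair, but the gap there is 0.6 points. Section 9.2.2 is the only statement more than one point out.

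Third, the slip could be in the control rate. Any rate from 10.1% to just under 12.7% would print as 18, and the upper end lies close to the 13% in 9.2.6, itself only a planning assumption. The margin is narrow, but the ordering rules this reading out unless 9.2.6 is also changed. Anyone with sustained abstinence under 9.7 is also verified abstinent at 3 months, so the 3-month rate cannot be lower than the sustained rate of 13%.

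Fourth, about 60% is the low end if more than 140 per arm are analysed. That is true, but 9.2.2 specifies 140, and 154 per arm still leaves power below 70%.

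**Conclusion.** The 18% in Section 9.2.2 is wrong on its printed inputs. The plan's formula gives 21.1 points, which agrees with 9.2.5. Power for 18 points falls short of the claimed 80% by 12 to 20 percentage points: 80 − 67.8 = 12.2 at 154 per arm by the plan's formula, and 80 − 59.6 = 20.4 at 140 per arm by exact enumeration. The error is in the favourable direction.

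This rests on two-sided testing and on the 20% control rate and 0.002 alpha being meant as printed. Changing to one-sided testing does not recover 18. The figure is consistent with the uncorrected alpha of 0.01, but the documents do not say how it arose, so that remains a conjecture. The point deserves correction, but it touches only the description of one secondary outcome.

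**What to change.** In Section 9.2.2, after confirming that the 20% control rate and the 0.002 alpha are intended, do one of two things:

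- restate the smallest detectable difference as 21%, matching 9.2.5; or
- keep 18% and state power of about 60% at 140 per arm.

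The sample size, alpha, test and primary power statement stay as they are, and Sections 9.2.3 to 9.2.6 need no separate correction for this point. The cost is one edited figure, and the stated sensitivity for this outcome becomes less favourable.

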
### 1.2.1 Current R01 preliminary findings (Smokefree Support Study 1).

The proposed study was informed by the recently completed RCT which Drs. [name] and [name] conducted at MGH and Memorial Sloan Kettering (MSK) to assess integration of an Intensive Treatment (IT; 11 sessions of motivational counseling, in-person and phone, plus choice of FDA-approved medication) versus MSK's usual care with recently diagnosed cancer patients (4 sessions of MI counseling plus FDA-approved medication advice). Among patients who are potentially eligible based on chart screen, approximately one-third enrolled; among known eligible smokers who agreed to be screened, 70% enrolled. Based on preliminary analyses as of February 2018, 303 patients were enrolled and randomized to a treatment arm (56%

female, mean age = 58; 82% white, non-Hispanic; 10 % Black; 5.0% Hispanic). This includes patients diagnosed with thoracic, head and neck, GI, GU, breast, lymphoma, melanoma, and ob/gyn cancers. Using intention-to-treat analyses counting non-responders as "smokers" (86% 6-month survey response rate and 87% cotinine validation response rate), cotinine validated 6-month abstinence rates are 19% in the Standard Care group and 33% in the Intensive Treatment group ( $p < .02$ ). Using intention-to-treat, 57% of Intervention Treatment group participants were adherent to sustained counseling (> 7 sessions), which was associated with increased 6-month quit rates ( $p < .0001$ ). These data support preliminary effectiveness of the proposed intervention treatment.

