9.6 Plans for analyzing the primary objectives: treatment effectiveness (Aim 1)

The primary objective is to compare the proportions of participants in the study arms with 7-day point-prevalence abstinence from cigarettes at 6-months post enrollment. We will define 7-day point-prevalence by saliva cotinine (< 15 ng/ml) or expired air CO (<10 ppm). All participants who report being quit and no NRT or e-cigarette use will be requested to provide saliva samples, expired air CO will be measured in participants who report being quit and report concurrent NRT or e-cigarette use. If a participant is lost to follow-up or does not provide a saliva or CO sample, they will be considered a current smoker. The primary analysis will be performed from an intent-to-treat perspective. Chi-square tests will be used to compare the outcomes between treatment groups. Outcomes will be considered different with  $p<0.01$ .

As a randomized study, it is hoped that the two groups will be balanced between potential confounders. Appropriate comparisons between the groups will be performed (chi-squared tests, t-tests, etc.) to identify any potential confounders that were not balanced. If significant areas of imbalance are identified, logistic regression modelling will be performed to adjust for potential confounding.

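### Sections 9.3 and 9.5/9.6 count deaths differently in the primary analysis, so the stated 80% power does not belong to the planned analysis; at 308 patients the chi-square has about 77% to 84%, depending on what the 15% and 32% rates mean

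*Combined protocol and SAP*

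**What the plan says.** - **Rates (9.1).** Six-month abstinence "will be 15% for the standard care group and 32% for the intervention group". The section derives these from the preceding trial and an earlier trial in low-income smokers. It does not say whether they apply to all randomized patients or to survivors.
- **Power (9.2.1).** "The study will have 80% power to detect a 17% difference in 7-day point-prevalence tobacco abstinence". The calculation is two-sided at alpha 0.01 and rests on 280 patients. The table beneath is headed as results for "Testing Two Proportions using the Z-Test with Unpooled Variance"; the row used has 140 per arm and power 0.80184.
- **Deaths (9.3, 9.4).** Under a heading about drop-outs and loss to follow-up: "We estimate that 10% of participants will die within 6-months of enrollment, so an additional 10% (n=28) will be recruited". The total is 308.
- **Missing outcomes (9.5).** Outcome analyses are intent-to-treat. Patients lost to follow-up are classified together with "those who do not provide a saliva or an expired air sample as current smokers". Section 9.6 repeats this rule for the primary endpoint.
- **Test (9.6).** "Chi-square tests will be used to compare the outcomes between treatment groups", at p<0.01.

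None of these sections says how a patient who died before the 6-month assessment enters the primary analysis.

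**The concern.** The sample-size section and the analysis sections imply different denominators. The allowance in 9.3 restores an analysis set of 280 after deaths are removed. Under 9.5 and 9.6 no one is removed: a patient who died gives no 6-month sample, and 9.3 itself places deaths under loss to follow-up, so the smoker rule applies with no written exception. At 10% mortality this concerns about 31 of 308 patients (308 × 0.10 = 30.8).

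How they are counted changes the denominator, both estimated abstinence rates and the power. If the choice is left open, it can be made after outcomes are known, and a non-significant result would be read against a power that belongs to another analysis set and another test.

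**Working it through.** **Inputs.** Rates 15% and 32% (9.1); two-sided alpha 0.01, so z = 2.576 (9.2.1); 140 per arm (9.2.1 table); 10% deaths and N = 308 (9.3, 9.4), i.e. 154 per arm at the 1:1 allocation of the table. Assumptions not in the documents: the same death share in both arms, and a chi-square without continuity correction.

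**Formulas.** With difference d, n per arm and mean rate p̄:
- SE_u = √{[p₁(1−p₁) + p₂(1−p₂)]/n}; SE_p = √{2p̄(1−p̄)/n}
- Unpooled z: power = Φ(d/SE_u − 2.576)
- Pooled chi-square: power = Φ((d − 2.576·SE_p)/SE_u)
- Exact: sum of binomial probabilities over all tables in which the Pearson chi-square rejects.

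**Step 1. The plan's own figure.** n = 140, d = 0.17, SE_u = 0.04965. 0.17/0.04965 − 2.576 = 0.848, and Φ = 0.8018. The table's figure is reproduced.

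**Step 2. Same patients, planned test.** SE_p = 0.05068. (0.17 − 2.576 × 0.05068)/0.04965 = 0.795, power 78.7%; exact 79.4%.

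**Step 3. Three readings of the deaths at N = 308.**

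(a) *Deaths counted as smokers, 15%/32% are survivor rates.* 0.15 × 0.9 = 13.5%; 0.32 × 0.9 = 28.8%; d falls from 17 to 15.3 points. With n = 154, SE_u = 0.04571 and SE_p = 0.04654: (0.153 − 2.576 × 0.04654)/0.04571 = 0.725, power 76.6%.

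(b) *Deaths excluded.* 308 × 0.9 = 277.2, about 139 per arm at 15%/32%.

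(c) *15%/32% already count deaths as smokers.* n = 154, d = 0.17, SE_u = 0.04734, SE_p = 0.04832: (0.17 − 2.576 × 0.04832)/0.04734 = 0.962, power 83.2%.

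| Reading | n per arm | Rates | Pooled | Exact chi-square | Unpooled z |
|---|---|---|---|---|---|
| Plan as stated | 140 | 15/32 | 78.7% | 79.4% | 80.2% |
| (a) | 154 | 13.5/28.8 | 76.6% | 77.3% | 78.0% |
| (b) | 139 | 15/32 | 78.3% | 79.0% | 79.8% |
| (c) | 154 | 15/32 | 83.2% | 83.8% | 84.5% |

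**Step 4. What drives reading (a).** Dilution of the difference, not the size of the allowance. Dividing instead of multiplying (280/0.9 = 311.1, so 312, or 156 per arm) gives 77.2% pooled at the diluted rates. Reaching 80% pooled there would take 165 per arm (330 in total).

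**Step 5. Sensitivity of (a) to the death share (assumed values, pooled, 154 per arm).** 5% deaths: 80.0%. 10%: 76.6%. 15%: 72.8%. A Yates-corrected chi-square at 10% would give 72.7% (exact).

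**The case against.** The strongest defence concerns the rates. Section 1.2.1 reports the preceding trial's 19% and 33% as obtained "Using intention-to-treat analyses counting non-responders as" smokers. If 15% and 32% inherit that convention and it covered deaths, they are all-randomized rates, power at 308 exceeds target, and surplus recruitment does no harm. This stands as a possibility, and it is why no single power figure can be asserted. It does not settle the plan: 1.2.1 does not mention deaths, and on this reading the reason 9.3 gives for the 28 extra patients falls away.

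It can also be said that deaths are not covered by the smoker rule. Section 7.1 schedules a vital-status update before each follow-up, so deaths can be told apart from non-response. The reference cited in 9.5 for possible completion weights concerns treatment comparisons among survivors. Both are true, but the weights are only to be considered, and no exclusion of deaths is written. On this reading power is 78% to 79% with the chi-square, and 79.8% with the plan's own unpooled method.

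Three stronger conclusions are tempting and are not supported:
- *That the trial simply has 77% power.* This needs deaths scored as smokers and 15%/32% as survivor rates. The first is the literal effect of the rule and the second is implied by 9.3; neither is stated.
- *That the 10% add-on was miscalculated and this causes the shortfall.* 308 versus 312 is four patients. It matters only if deaths are excluded, which is not the reading that gives 77%.
- *That using an unpooled z-test undermines the sample size.* The pooled approximation needs 144 per arm rather than 140; exact enumeration of the chi-square already reaches 80.2% at 142.

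**Conclusion.** The point holds as an inconsistency about the analysis set, with a moderate effect on power. Section 9.3 treats deaths as leaving the 280; 9.5 and 9.6, read literally, keep them as smokers. With the planned chi-square at alpha 0.01 and 308 patients, power is about 77% if 15%/32% are survivor rates and deaths count as smokers, 78% to 79% if deaths are excluded, and 83% to 84% if the rates already include deaths. The 80% is correct for the calculation shown in 9.2.1, but that calculation uses a different test and, on the evidence of 9.3, a different set of patients from the planned analysis.

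The figures assume 10% deaths in each arm, equal allocation and no continuity correction. The primary test and alpha are unaffected. What is missing is a rule for about 31 patients on the primary endpoint and a power statement that matches it.

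**What to change.** - In 9.3 and 9.6, state that all 308 randomized patients are analysed and that deaths before the 6-month assessment count as non-abstinent in both arms.
- In 9.1, state whether 15% and 32% include deaths.
- Restate 9.2.1 for the planned chi-square at 154 per arm: about 77% if the rates are among survivors (13.5% versus 28.8% over all randomized), or about 83% to 84% if they already include deaths. In the second case, reword 9.3, since the extra 28 are then not needed to protect power. Say whether a continuity correction is used.
- Add a sensitivity analysis among patients alive at 6 months. The complete-case analysis in 9.5 does not separate deaths from other missing outcomes.
- Keep N at 308.

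The cost is wording plus one sensitivity analysis, with no extra patients. The downside is that the stated power may become about 3 points less favourable. The wording should be settled before outcomes by arm are seen.
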